*****Please see attached FDA 510-approved device brochure- specific to the ultrasound equipment used in this study**

## Gastroenteritis Statistical Plan

We calculated the sample size required to provide more than 80% power (with a two-sided alpha level of 0.05) to detect an absolute difference of 15% in PO vs. IV rehydration or more between groups. We estimated a sample size of 200 patients for the gastroenteritis section of the study.

Enrolled Patients are to be randomized to immediate versus delayed US assessment of the IVC in patients aged 0-21 years who presented to an emergency department with vomiting requiring ondansetron or with diarrhea possibly requiring IV rehydration. Patients enrolled were randomized to assessment of dehydration by clinical exam plus US (immediate) or clinical exam alone and then US 15 minutes later (delayed). Clinical dehydration scores were recorded prior to IVC US. Decision to treat with IV versus PO rehydration, pre-test and post-test probabilities were recorded before and after US. Primary outcomes included IV versus PO rehydration based on intent-to treat principle; secondary outcomes included median total ED length of stay (EDLOS; triage time to disposition) time failure of PO rehydration, and disposition (ED discharge vs admission). All outcomes between groups were compared by using a Pearson chi-squared test. The alpha level was set at .05 for all analyses, 95% CIs were calculated, and all comparisons were two tailed. Data analysis was performed with the use of SPSS 20.0 (IBM).

We calculated the sample size required to provide more than 80% power (with a two-sided alpha level of 0.05) to detect an absolute difference of 15% more more between arms in the number of patients receiving antibiotics with 60 minutes between groups. We estimated a sample size of 200 patients for the sepsis section of the study.

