Using the following equation to calculate sample size for proportional outcomes in randomized controlled trials and using data from a 2012 study by Paul et. al. citing a 58% overall compliance with PALS severe sepsis target times:

$$m \text{ (size per group)} = c \times \frac{\pi_1(1 - \pi_1) + \pi_2(1 - \pi_2)}{(\pi_1 - \pi_2)^2}$$

where c is set at 7.9 for a power of 80%

π_1 is current percent success rate on standard protocol

π_2 is the current percent success plus the anticipated treatment effect percent

We have calculated the total number of subjects in the sepsis arm to be: 82 per group or 164 total patients for a power of 80% and a type I error set at 5%

For the gastroenteritis and dehydration arm we have established a sample size using the following power calculation for continuous (time) outcomes

	Protocol Name:	Randomized Controlled Trial of Inferior Vena Cava Ultrasonography in the Management and Disposition of Pediatric Patients Undergoing Evaluation for Sepsis and Dehydration
	Principal Investigator:	[name] [contact] [contact] or [contact]
	Primary Contact Name/Contact Info:	[name] [contact]
	Date Revised:	2/10/2015
	Study Number:	IF1733382

$$\text{Total sample size} = \frac{c}{\delta^2} + 2$$

where c is set at 7.9 for a power of 80%

δ^2 is set for a 10% size treatment effect (reduction in time)

We would need 200 subjects per group or a total of 400 patients in the gastroenteritis arm of the study.

d) Study Timelines

Currently the Mount Sinai Pediatric Emergency Department sees approximately 30,500 patients on an annual basis. Of this total census about 200 trigger the Stop Sepsis alert upon registration. Based on this we have set the enrollment period over 12 months.

Current census data predicts approximately 3000 Mount Sinai annual emergency department visits for vomiting and dehydration requiring antiemetic therapy. In order to collect a convenience sample of 400 patients and adjust for seasonal variability, the study period will enroll over a six month period between June 2015 and November 2015.

e) Study Endpoints

For the Sepsis arm endpoints include:

Primary

- Secured second vascular access point- type (IO, second IV, CV access) within 15 min of physician evaluation
- Inotrope/Vasopressor use
- Antibiotic within 60 min

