## Sepsis Statistical Plan

Enrolled Patients are to be randomized to immediate versus delayed US assessment of the IVC in patients aged 0-21 years who presented to an emergency department with a STOP SEPSIS triage alert and clinical concern for sepsis. Patients enrolled were randomized to assessment of sepsis by clinical exam plus US (immediate) or clinical exam alone and then US 15 minutes later (delayed). Pre-test probability of sepsis were recorded prior to IVC US. Decision to initial sepsis protocol/pathway, pre-test and post-test probabilities were recorded before and after US. Primary outcomes included proportion of patients receiving antibiotics within 60 minutes based on intent-to treat principle; secondary outcomes include median total ED length of stay (EDLOS; triage time to disposition), time to secured vascular access, and vasopressor use. All outcomes between groups were compared by using a Pearson chi- squared test. The alpha level was set at .05 for all analyses, 95% CIs were calculated, and all comparisons were two tailed. Data analysis was performed with the use of SPSS 20.0 (IBM).

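### The SAP assigns Pearson's chi-squared test to every outcome but does not say how ED length of stay and time to vascular access are to be put into categories

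*SAP*

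**What the plan says.** The SAP's Gastroenteritis Statistical Plan states: "All outcomes between groups were compared by using a Pearson chi-squared test". Its outcome list includes a time: "secondary outcomes included median total ED length of stay (EDLOS; triage time to disposition". The Sepsis Statistical Plan repeats the rule, "All outcomes between groups were compared by using a Pearson chi- squared test", and lists two times: "secondary outcomes include median total ED length of stay (EDLOS; triage time to disposition), time to secured vascular access, and vasopressor use". Neither section gives a cut-off for these times, a grouping rule, or a rank, t or survival test. The only time threshold in the SAP text available is the 60-minute one in the sepsis primary outcome (antibiotics), which is a different variable. Each section also sets a two-sided 5% level and calls for confidence intervals: "The alpha level was set at .05 for all analyses, 95% CIs were calculated, and all comparisons were two tailed".

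The protocol treats time as continuous. Section 5(c) sizes the gastroenteritis arm with a "power calculation for continuous (time) outcomes", in which the squared effect "is set for a 10% size treatment effect (reduction in time"). Section 5(e) defines length of stay as a duration without a threshold, and lists it among the primary endpoints of the gastroenteritis arm. For sepsis, section 5(e) lists a related primary endpoint that does have a threshold: "Secured second vascular access point- type (IO, second IV, CV access) within 15 min of physician evaluation".

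One part of the SAP is missing from the text available, so a rule stated there cannot be excluded.

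**The concern.** Pearson's chi-squared compares counts in categories. A duration has to be cut before the test can be applied, and the result depends on where it is cut. The SAP specifies a test for length of stay and for time to vascular access but not the step that makes the test possible. Someone running the analysis must add a split or use another test.

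Two things are at stake. First, a split discards information that a rank test keeps. Second, unless the rule is fixed before analysis, the test or the cut-off could be chosen with the data in view. The SAP calls these outcomes secondary, which limits the damage, but the protocol gives length of stay primary status in the gastroenteritis arm.

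**Working it through.** The plan has no figure of its own to reproduce on this point. The defect is textual; the arithmetic only shows its size.

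**1. Which outcomes are affected.**

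| Outcome in SAP | Type | Chi-squared usable as written? |
|---|---|---|
| IV vs PO rehydration (gastroenteritis primary) | binary | yes |
| Antibiotics within 60 minutes (sepsis primary) | binary | yes |
| Disposition; vasopressor use; failure of PO rehydration, read as yes/no | categorical | yes |
| ED length of stay (both sections) | duration | no, needs a split |
| Time to vascular access (sepsis) | duration as worded | no, needs a split |

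**2. Efficiency of a pooled-median split for length of stay.** Assume log-normal times. Relative to the t-test on logs, the large-sample efficiency is 2/π = 0.637 for the median split and 3/π = 0.955 for Wilcoxon. The ratio is (2/π)/(3/π) = 0.667. So 200 patients analysed with the split carry about the information of 200 × 0.667 = 133 analysed with Wilcoxon. This depends on log-normality and small effects, not on the spread.

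**3. Size of the pooled-median split.** Take n per arm and no ties. If k patients in one arm lie above the pooled median, the 2×2 statistic is 2(2k − n)²/n, and under no effect k is hypergeometric. The 5% critical value is 3.841.
- n = 100: k = 56 gives 2 × 12²/100 = 2.88; k = 57 gives 2 × 14²/100 = 3.92. Rejection is at k ≥ 57 or k ≤ 43, with probability 6.6%.
- n = 200: k = 109 gives 2 × 18²/200 = 3.24; k = 110 gives 2 × 20²/200 = 4.00. Rejection is at k ≥ 110 or k ≤ 90, with probability 5.7%.

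Both exceed the SAP's 5%.

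**4. Illustrative power.** Inputs from the documents: 100 per arm (the SAP's 200 gastroenteritis patients, taken as a total split 1:1), 200 per group (protocol 5(c), gastroenteritis), and a 10% reduction in time (protocol 5(c)), read here as a ratio of 0.9. Assumed: log-normal times with CV 0.5, 0.6 or 0.8, because the documents give no SD or CV. Power is from 20,000 simulated trials per setting, two-sided 5%.

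| Per arm | CV | Wilcoxon | Median split | Loss (points) |
|---|---|---|---|---|
| 100 | 0.5 | 33.2% | 27.9% | 5.3 |
| 100 | 0.6 | 25.6% | 22.1% | 3.5 |
| 100 | 0.8 | 17.7% | 16.4% | 1.3 |
| 200 | 0.5 | 58.7% | 45.4% | 13.3 |
| 200 | 0.6 | 45.9% | 35.0% | 10.9 |
| 200 | 0.8 | 30.5% | 23.9% | 6.6 |

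The split runs above 5% size, so these losses are if anything understated.

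The same ratio in sample-size terms, for 80% power: n per arm = 2 × 7.85 × σ²/(ln 0.9)², times π/3 for Wilcoxon or π/2 for the split. With CV 0.5, σ² = ln(1.25) = 0.223 and (ln 0.9)² = 0.0111, so the base is about 315.5, giving 330 and 496. CV 0.6 gives 455 and 683; CV 0.8 gives 733 and 1,099.

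**5. Sensitivity to a fixed cut-off.** Assume a control median of 200 minutes, log-SD 0.5, stays 20% shorter and 100 per arm (2,000 simulated trials). Power is 0.86 for the rank test and 0.74 for the pooled-median split. For fixed cuts at 120, 180, 240 and 360 minutes it is 0.60, 0.73, 0.65 and 0.42. An unstated cut-off is therefore not a detail.

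**The case against.** The best defence concerns length of stay. An outcome described as a median and compared by Pearson chi-squared is a fair description of the median test. Its cut-off is set by rule, without regard to arm, so nothing is left to choose after the fact. That is a coherent reading, and preferring Wilcoxon is then partly a matter of efficiency. What remains is that the SAP does not state it, that the split exceeds the nominal size, and that no median is named for vascular access.

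For vascular access, the SAP line may be loose shorthand for the protocol's 15-minute endpoint, which is binary, has an origin (physician evaluation) and suits chi-squared. Antibiotic timing and vasopressor use, also sepsis primaries in the protocol, reappear in the SAP, which makes this plausible. Against it, the SAP words the outcome as a time and does not mention a second access point. The documents do not settle the matter, so the two descriptions must be reconciled; neither reading can be ruled out.

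The numbers also have limits. The 10% effect and 200 per group are gastroenteritis figures. The protocol's sepsis size of 82 per group was not modelled, and nothing here quantifies vascular access. Even the meaning of the 10% is unsettled: the protocol's formula with 0.10 gives 7.9/0.01 + 2 = 792, not its stated total of 400.

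A reader might go further and apply chi-squared to unsplit times. With 200 distinct values the statistic is always 200 on 199 degrees of freedom (p = 0.467), whatever the data. That is a bound, but an unlikely analysis, and the SAP need not be read as intending it.

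**Conclusion.** The point holds and should be fixed. As written, the stated test does not fit ED length of stay in either section, or time to vascular access in the sepsis section if that outcome is a time. This conclusion rests on the text alone, subject to the part of the SAP not available.

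The size is moderate. On the most favourable reading for length of stay, the efficiency is about two-thirds of Wilcoxon's (log-normal times, large samples) and the type I error is 6.6% at 100 per arm or 5.7% at 200. Under the assumed CVs and a 10% shorter stay, the power loss is 1 to 5 points at 100 per arm, where neither test is well powered, and 7 to 13 points at 200 per arm.

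Two stronger inferences are not supported. One is that the main comparisons are compromised: both SAP primary outcomes and the categorical secondary outcomes suit chi-squared. The status of length of stay does need care, because the protocol makes it a gastroenteritis primary endpoint. The other is that the test or cut-off was, or must be, picked after seeing the data: a pooled-median rule would leave no choice, and a SAP can be clarified before analysis. The risk is conditional on the rule staying open.

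**What to change.** In each SAP section:

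- Limit Pearson's chi-squared to binary and categorical outcomes.
- Compare ED length of stay with the Wilcoxon rank-sum test, and report the Hodges-Lehmann difference with the 95% confidence interval that the SAP already promises. If a median split is really intended, say so, give the cut-off rule in advance, and deal with its size.

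In the sepsis section, first reconcile the SAP's time to vascular access with the endpoint in protocol section 5(e). If the outcome is binary, state the cut-off and keep chi-squared. If it is a time, state the origin and use either a rank test with patients who never get access ranked last, or a log-rank test with a stated rule for those patients.

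The cost is one or two sentences per section, written before analysis. Length of stay needs only the triage and disposition times that define it. For vascular access, the chosen origin must be a time that the study records; the documents do not settle this.

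### Protocol and SAP size the trial inconsistently, and the SAP's sepsis power claim rests on no rate in the available text

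*SAP*

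**What the plan says.** **Sepsis, Protocol 5c (Number of Subjects).** The calculation uses a two-proportion formula with constant 7.9 and a planning rate taken from a published study, "citing a 58% overall compliance with PALS severe sepsis target times". The result is "82 per group or 164 total patients for a power of 80% and a type I error set at 5" percent. The treatment effect behind it is not stated.

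**Sepsis, SAP.** The sizing paragraph is printed at the end of the Gastroenteritis Statistical Plan. It claims power above 80% at two-sided 0.05 to "detect an absolute difference of 15% more more between arms in the number of patients receiving antibiotics with 60 minutes between groups", and then: "We estimated a sample size of 200 patients for the sepsis section of the study". The Sepsis Statistical Plan names the matching endpoint: "Primary outcomes included proportion of patients receiving antibiotics within 60 minutes based on intent-to treat principle".

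**Gastroenteritis.** Protocol 5c sizes this cohort on a continuous time outcome with a 10% reduction, and arrives at 200 per group, 400 in total. The SAP sizes it to "detect an absolute difference of 15% in PO vs. IV rehydration or more between groups", and states: "We estimated a sample size of 200 patients for the gastroenteritis section of the study".

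**Interim look, Protocol 5i.** A safety look is set at a quarter of enrolment, given as 40 sepsis and 100 gastroenteritis patients.

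The available SAP text gives no control rate and no number per group for either cohort. Part of the SAP, ahead of the Gastroenteritis Statistical Plan, was not available for review.

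**The concern.** The SAP pairs a smaller sepsis effect than the one implied by the protocol with only 36 more patients (200 − 164), yet claims at least as much power. That cannot hold at the protocol's planning rate if 200 is the total. It can hold at other rates, but the available text names none, so the claim cannot be checked.

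Separately, the two documents give different recruitment targets and sizing outcomes, and the available text does not explain the change. Three things are at stake: which target governs the end of recruitment, how a null sepsis result should be read, and what a quarter of enrolment means for the safety look.

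**Working it through.** **Inputs.** Two-sided alpha 0.05, difference 15 points, 200 patients (SAP); 58%, constant 7.9, 82 per group (Protocol 5c); Pearson chi-squared test (SAP). Equal allocation is assumed for the SAP, as in 5c. Neither sizing text allows for dropout, and none is applied.

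**Step 1: reproduce the protocol's 82.** m = 7.9 × [p1(1−p1) + p2(1−p2)] / (p1−p2)².
- 58% vs 78%: 7.9 × (0.2436 + 0.1716) / 0.04 = 82.0. This matches, so the implied effect is 20 points.
- 58% vs 73%: 7.9 × (0.2436 + 0.1971) / 0.0225 = 154.7, so 155 per group, 310 in total.
- 75% vs 90%: 7.9 × (0.1875 + 0.0900) / 0.0225 = 97.4.

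**Step 2: power for 15 points if 200 is the total (n = 100 per group).** With p̄ the mean of the two rates,

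power = Φ{ [0.15 − 1.96·√(2p̄(1−p̄)/n)] / √([p1(1−p1) + p2(1−p2)]/n) }.

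At 58% vs 73%, p̄ = 0.655. The numerator is 0.15 − 1.96 × 0.0672 = 0.0182, the denominator is 0.0664, the ratio is 0.275, and power is 60.8%. Exact enumeration of the Pearson test gives 61.0%.

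| Lower rate | Higher rate | Power |
|---|---|---|
| 5% | 20% | 90% |
| 10% | 25% | 80.2% |
| 25% | 40% | 62% |
| 42.5% | 57.5% | 56% (minimum) |
| 58% | 73% | 61% |
| 65% | 80% | 66% |
| 70% | 85% | 72% |
| 75% | 90% | 80.2% |
| 80% | 95% | 90% |

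Power reaches 80% only at a lower rate of about 10% or less, or about 75% or more. It goes on rising beyond the ends of the table, to about 98% at 85% vs 100%. At the minimum, exact enumeration gives 59% rather than 56%.

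**Step 3: other readings, from 58%.**
- 100 per group: 80% power needs about 18.5 points.
- 82 per group: 52% power for 15 points; 80% power needs about 20 points.
- 200 per group: 89% power for 15 points, and at least 85% whatever the rate.

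**Step 4: sizes side by side.**

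| | Protocol 5c | SAP, 200 as total | SAP, 200 per group |
|---|---|---|---|
| Sepsis, total | 164 | 200 | 400 |
| Gastroenteritis, total | 400 | 200 | 400 |
| Gastroenteritis, sizing outcome | time | IV vs oral proportion | IV vs oral proportion |
| Interim at 40 sepsis | 24% | 20% | 10% |
| Interim at 100 gastroenteritis | 25% | 50% | 25% |

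Sepsis differs from the protocol in both SAP columns. The gastroenteritis count differs in one; its sizing outcome differs in both.

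**The case against.** **The SAP statement may be true.** A reader might infer from the 61% that the SAP made an arithmetic error, or that the sepsis cohort is underpowered. The documents do not show either. Rates of 75% vs 90% give 80.2% power with exactly 100 per group, so the authors may have used such a pair. Per group, 200 would satisfy the claim at any rate. This objection stands: what can be shown is an unsupported claim, not a wrong one.

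**The 58% belongs to another outcome.** It is overall compliance with target times, and the SAP's outcome is antibiotics alone. If overall compliance means that every target was met, the antibiotic rate can be no lower and may be well above 58%, where power rises. The protocol does not define it. This stands too, so the 61% is illustrative.

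**The gastroenteritis counts may agree.** If the SAP's 200 is per group, it matches the protocol's 400. That is possible. But the SAP speaks of patients for a whole section of the study, and Protocol 5d expects only about 200 sepsis alerts a year with 12 months of enrolment. Both favour a total. The difference in sizing outcome remains on either reading.

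**The interim look still works.** It is set by count and concerns safety, with no efficacy test described. That is fair: moving from 24% to 20% in sepsis matters little, and only gastroenteritis at 50% would be a notable shift.

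**A rate may stand in the unavailable part of the SAP.** This cannot be excluded. It would settle the power question but not the conflict in sepsis size.

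**Conclusion.** The inconsistency is established and should be fixed. Without assuming any rate, sepsis is 164 in the protocol against 200 or 400 in the SAP, and gastroenteritis is sized on time in one document and on a proportion in the other. The gastroenteritis count conflicts (400 vs 200) on the natural reading of 200 as a total.

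The SAP's sepsis power is unsupported rather than disproved. With 100 per group it lies anywhere from about 56% upwards, depending on a rate that the available text does not give. At the only documented planning rate it is about 61%, so a true 15-point difference would be missed about 39% of the time, and a null result could be over-read. That figure rests on two assumptions: that 200 is the total, and that 58% carries over to antibiotics within 60 minutes.

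Nothing here biases the treatment estimate or the test, and the point should not be read as saying so.

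**What to change.** Make Protocol 5c and the SAP state, for each cohort, one number per group, one primary outcome for sizing, one effect, and one control rate with its source. Then restate the power that follows. For sepsis:
- 58% kept, 100 per group: about 61% power for 15 points, or 80% for about 18.5 points.
- 58% kept, 82 per group: about 52% power for 15 points, or 80% for about 20 points.
- 75% vs 90% assumed and sourced, 100 per group: 80.2% power.
- 200 per group intended: say so; power for 15 points is at least 85% at any rate.

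For gastroenteritis, say whether 200 is the total or per group, and whether the sizing outcome is time or the IV versus oral proportion. Then restate the interim counts in Protocol 5i as 25% of the agreed totals.

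The cost is wording in both documents. No extra patients are needed. The downside is that the stated sepsis power may become less favourable.

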## Sepsis Statistical Plan

Enrolled Patients are to be randomized to immediate versus delayed US assessment of the IVC in patients aged 0-21 years who presented to an emergency department with a STOP SEPSIS triage alert and clinical concern for sepsis. Patients enrolled were randomized to assessment of sepsis by clinical exam plus US (immediate) or clinical exam alone and then US 15 minutes later (delayed). Pre-test probability of sepsis were recorded prior to IVC US. Decision to initial sepsis protocol/pathway, pre-test and post-test probabilities were recorded before and after US. Primary outcomes included proportion of patients receiving antibiotics within 60 minutes based on intent-to treat principle; secondary outcomes include median total ED length of stay (EDLOS; triage time to disposition), time to secured vascular access, and vasopressor use. All outcomes between groups were compared by using a Pearson chi- squared test. The alpha level was set at .05 for all analyses, 95% CIs were calculated, and all comparisons were two tailed. Data analysis was performed with the use of SPSS 20.0 (IBM).

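### Both primary outcomes are tested unadjusted although randomisation is stratified by severity: adjust for the stratum, and for the pre-scan ratings only if they are fixed before allocation

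*SAP*

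**What the plan says.** **Analysis.** The SAP's gastroenteritis plan states: "All outcomes between groups were compared by using a Pearson chi-squared test". Its sepsis plan says the same, and adds: "The alpha level was set at .05 for all analyses, 95% CIs were calculated, and all comparisons were two tailed". Neither names a covariate or a stratified analysis. The primaries are IV versus PO rehydration, and antibiotics within 60 minutes.

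**Information collected.** In the sepsis plan: "Pre-test probability of sepsis were recorded prior to IVC US". In the gastroenteritis plan: "Clinical dehydration scores were recorded prior to IVC US", and pre-test probabilities are recorded there too.

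**Randomisation.** Protocol 5(f) randomises the two cohorts separately and stratifies each by disease severity, giving SIRS criteria and the Clinical Dehydration Score as example scales.

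**Timing of the scan.** Protocol 5(a) and 5(f) scan the immediate arm before full clinical assessment and the control arm after 15 minutes of assessment and management. The clinician who enrols also randomises and completes the data forms.

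**The concern.** Both primaries are treatment decisions, and protocol 5(f) leaves treatment to the clinician's discretion. Severity, and the clinician's own judgement before the scan, are natural predictors of those decisions, although the documents do not say how strong they are. A test that ignores a predictive baseline variable has less power than one that uses it. A factor important enough to stratify on would normally also appear in the analysis.

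The opposite risk is adjusting for the wrong thing. A covariate is safe only if allocation cannot have influenced it. The SAP ties the ratings to the scan, and scan timing is exactly what differs between the arms.

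**Working it through.** **Inputs.** Two-sided alpha is 0.05 and the effect is 15 points (SAP). The sample size is 200 for each cohort, with no statement of total or per arm (SAP). The SAP gives no control rate. The only rate in either document is 58% (protocol 5(c)). It is overall compliance with severe-sepsis target times, not antibiotics alone, so using it here is an assumption. R-squared between covariate and outcome is also assumed, over 0.05 to 0.30.

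**1. The SAP's own figure.** With p1 = 0.58 and p2 = 0.73, the mean rate is 0.655.

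n per arm = [1.96 × √(2 × 0.655 × 0.345) + 0.8416 × √(0.58 × 0.42 + 0.73 × 0.27)]² / 0.15² = (1.3177 + 0.5587)² / 0.0225 ≈ 157.

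So 200 in total is not reproduced at 58%. A need of 100 per arm arises at 10% versus 25% or at 75% versus 90%. Without a control rate, the 200 cannot be derived from the SAP's inputs.

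**2. Unadjusted power at 100 per arm.** z = (0.15 × √100 − 1.3177) / 0.6639 = 0.275, which gives 60.8%.

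**3. Gain from a true baseline covariate.** Adjustment acts roughly like a sample of n / (1 − R²). For 100 per arm that is 105.3, 111.1, 125.0 and 142.9 at R² of 0.05, 0.10, 0.20 and 0.30. Power:

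| Rates, n per arm | R² 0 | 0.05 | 0.10 | 0.20 | 0.30 |
|---|---|---|---|---|---|
| 58% v 73%, 100 | 60.8% | 63.1% | 65.4% | 70.6% | 76.3% |
| 42.5% v 57.5%, 100 | 56.5% | 58.7% | 61.0% | 66.1% | 72.0% |
| 10% v 25%, 100 | 80.2% | 82.2% | 84.2% | 88.2% | 92.0% |
| 58% v 73%, 200 | 88.7% | 90.2% | 91.7% | 94.4% | 96.7% |

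Simulation agrees with the first row. A linear probability model with robust standard errors moved power from 61% to 66% (R² about 0.10), 62% to 71% (about 0.18) and 61% to 76% (about 0.28), with type I error of 5.1–5.5%. A logistic model gave 66%, 72% and 76% at R² of about 0.13, 0.22 and 0.30.

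**4. What happens if the rating follows allocation.** The setting is 100 per arm, 58% in both arms, and a covariate whose mean differs between arms only because of when it was recorded. Type I error of the adjusted test (linear probability model):

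| Shift between arms | R² 0.10 | 0.20 | 0.31 |
|---|---|---|---|
| 0.2 SD | 7.8% | 11.0% | 16.3% |
| 0.3 SD | 11.1% | 17.9% | 30.4% |
| 0.5 SD | 22.0% | 40.0% | 63.2% |

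The unadjusted test stayed at 4.9–5.7%. At 0.3 SD the adjusted model reported a spurious difference of 4.8, 6.6 and 8.2 points respectively. A separate simulation put the 0.3 SD error at about 14–27%. The size of any real shift is unknown.

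**5. Which covariate is safe.** The severity stratum must be known before a stratified allocation can be made, so it qualifies. The SAP's ratings qualify only if they too precede allocation, and the SAP does not say so. If the Clinical Dehydration Score defines the stratum, a pre-allocation value exists, but the protocol offers it only as an example.

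**The case against.** The strongest reply is that an unadjusted chi-squared on a randomised binary outcome is valid, so adjustment is an efficiency choice and not the correction of an error. That stands. It also stands that, on the documents as written, the chi-squared is safer than a model containing the pre-scan ratings.

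Four stronger readings are tempting and are not supported:

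- **That the gain is free.** It is free only for a value fixed before allocation. Being recorded before the scan does not establish that.
- **That the ratings exist for every patient.** The SAP makes no statement about completeness.
- **That the cohorts have no power to spare.** This depends on reading 200 as a total and on borrowing the 58%. At 200 per arm, or at 10% versus 25% with 100 per arm, power is 80% or more without adjustment. No IV-versus-PO control rate appears anywhere.
- **That the protocol's 82 per group can be judged against the SAP's 15 points.** The protocol formula returns 82 at a 20-point effect: 7.9 × (0.58 × 0.42 + 0.78 × 0.22) / 0.20² = 82.0. Pairing 82 with 15 points describes neither document's design.

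The gain from the severity stratum alone was not computed separately. A severe/not-severe split would probably carry less information than a graded score, so the lower R² values are the more cautious guide.

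**Conclusion.** The point holds as a recommended improvement. The primary analyses omit the severity factor used in randomisation, and they omit graded ratings that could help if their timing were secured. At 100 per arm and 58% versus 73%, the gain is about 2 to 5 points of power for R² of 0.05 to 0.10, and 10 to 16 points for 0.20 to 0.30. Even at 0.30, power reaches only 76%, so adjustment would not cure a sample-size shortfall if 200 is a total. If 200 is per arm, the gain at those rates is at most 8 points, from about 89%.

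These sizes rest on an assumed R² and on a 58% rate that measures something other than antibiotic timing. That adjusting for the stratum is safe does not depend on either assumption. Adjusting for the ratings is safe only if they precede allocation.

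**What to change.** In each cohort's SAP section:

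1. Make the primary analysis a logistic model with arm and the severity stratum as used in the randomisation, and state how the stratum is defined. Report a covariate-standardised risk difference with a 95% CI, which keeps the SAP's absolute-difference scale. Keep the Pearson chi-squared as a sensitivity analysis.
2. Add the pre-test probability (both cohorts) and the graded Clinical Dehydration Score (gastroenteritis) only if the form records and time-stamps them before allocation is revealed. State how missing values are handled.
3. If pre-allocation recording cannot be shown, adjust for the stratum alone.

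Cost: about one SAP sentence per cohort, one line on the data form, and slightly more analysis work to obtain the standardised difference and its interval. No extra patients or procedures are needed.
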